### *Expected survey precision*

Since the request of survey results at district level for some indicators, the sample allocation

adopted is an equal size allocation, with 438 expected women interviews for all the districts except the three districts in Kigali province, which is the **maximum sample size allowable**. For the three districts in Kigali province, 548 expected women interviews were allocated to each district taking into account that the fertility rate is lower in the capital city than in other areas. With the current sample design, the following tables provide the expected survey precision for women survey at national level, province level and district level. The relative standard error (CV) for a proportion P is calculated by the following formula:

$$CV = \frac{Deft * \sqrt{P*(1-P)/n}}{P}$$

At national level, the relative standard error will be under 5% for all indicators of 10% or above which is a very good precision; at province level, since the sample size varies according to the number of districts per province, the precision for an indicator at 10% or above will have a relative standard error under 10% which is a good precision at survey domain level; at district level, the precision for an indicator at 10% or above will have a relative standard error under 20% which is acceptable as precision for second level domains.

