With the request of representative results for some indicators at district level, the total sample size is tight and therefore an equal size allocation was adopted, with a slightly larger sample size for the districts in the Kigali City because of the low fertility level in Kigali City. In fact, the equal size allocation is not far from the proportional allocation which is the best allocation, because the district sizes are quite homogeneous. On the other hand, the total sample size is already large; any substantial increase in the total sample size in order to provide representative results for most of the indicators at district level will compromise the data quality due to the longer duration of field data collection or larger number of field workers. With the current sample size, adequate survey precision at district level will be obtained for women indicators above 15%; and for children (under five) indicators above 20%.

The expected survey results are calculated based on the survey results of the RDHS 2010: these are included the average number of women 15-49 per household; the average number of men 15-59 per household; household response rate and women individual response rate that will be more than 99 percent; men individual response rate that will be more than 98 percent; the response rate to HIV testing that will be more than 98 percent for both men, women, and children and young adults.

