#### **Expected precision at province level for an indicator P=10%**

(Assuming a design effect of Deft=1.5)

Province	# of women interviews	SE	CV	%95 Confidence limits	
				Lower	Upper
East	3,066	0.008	0.08	0.084	0.116
Kigali	1,644	0.011	0.11	0.078	0.122
North	2190	0.010	0.10	0.081	0.119
South	3,504	0.008	0.08	0.085	0.115
West	3,066	0.008	0.08	0.084	0.116

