### Expected precision at district for different indicator levels

(With an estimate of 440 women interviews and assuming a design effect of Deft=1.5)

Indicator level	SE	CV	%95 Confidence limits	
			Lower	Upper
0.10	0.022	0.22	0.057	0.143
0.15	0.026	0.17	0.099	0.201
0.20	0.029	0.14	0.143	0.257
0.25	0.031	0.12	0.188	0.312
0.30	0.033	0.11	0.234	0.366

As for the precision of HIV testing, since Rwanda is a low HIV prevalence country, HIV testing must be included in a high proportion of the households sampled for the survey. HIV testing will be conducted in the sub-sample households for men survey; consisting one of every two households selected for the household and women survey. The sample for the RDHS-V is designed to measure the prevalence of HIV within  $\pm 0.5$  percentage points at the national level and generally within  $\pm 1$  percentage point at the province level. The confidence interval for Kigali City is expected to be somewhat larger than that of the other provinces due to its higher prevalence estimate; however, the relative error for the Kigali City estimate is expected to be equal to or less than that of the other provinces. Compared to the last RDHS-IV (2010), the precision of HIV testing will be similar due to the same sample size.

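### At P = 10%, Kigali province and the 27 districts with 438 women miss the precision bounds stated in the protocol's text, by its own formula and tables

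*Protocol*

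**What the plan says.** The section Expected survey precision introduces its tables as precision for the women's survey at national, province and district level. It fixes the sample at "438 expected women interviews for all the districts except the three districts in Kigali province", and at 548 in each of those three. It then gives the method: "The relative standard error (CV) for a proportion P is calculated by the following formula", namely Deft × √(P(1−P)/n) divided by P.

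The text draws three conclusions for indicators at 10% or above:

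- Nationally, the relative standard error is under 5%.
- For provinces, "the precision for an indicator at 10% or above will have a relative standard error under 10" per cent.
- For districts, "at district level, the precision for an indicator at 10% or above will have a relative standard error under 20" per cent.

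No province or district is excepted.

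The tables that follow show something different at the 10% level. The province table ("Expected precision at province level for an indicator P=10" per cent, "Assuming a design effect of Deft=1.5") prints a CV of 0.11 for Kigali. The district table ("With an estimate of 440 women interviews and assuming a design effect of Deft=1.5") prints 0.22.

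Two other places set a higher district threshold. Structure of the sample and the sampling procedure says "adequate survey precision at district level will be obtained for women indicators above 15" per cent. Appendix B lists a minimum level for each indicator, 15% for most women's individual indicators, and ties those minima to a district relative standard error of 20%.

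**The concern.** The text and the tables describe the same design, formula and design effect, so they should agree. At P = 10% they do not, and the text is the more favourable of the two.

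These sentences tell a reader which domain estimates can be relied on. Someone using the text alone would accept a district indicator between 10% and about 11.4%, or a Kigali province indicator between 10% and about 12.0%, as meeting a precision standard that it misses. The text also puts the district threshold at 10%, while two other places in the protocol work with 15% for most women's indicators.

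**Working it through.** **Inputs, all from the protocol.** Deft = 1.5 (table captions). n = 438 in each of 27 districts and 548 in each of the three Kigali districts (Expected survey precision). Province n from the province table. National n = 13,470 (national table).

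**Allocation check.** 27 × 438 + 3 × 548 = 11,826 + 1,644 = 13,470, which matches the national table. Kigali province is 3 × 548 = 1,644, which matches the province table.

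**Formula.** CV = 1.5 × √(P(1−P)/n) / P = 1.5 × √((1−P)/(nP)). At P = 0.10 this becomes 1.5 × √(9/n).

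**Results at P = 10%.**

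| Domain | n | CV computed | CV printed | Bound in text | Met? |
|---|---|---|---|---|---|
| National | 13,470 | 3.9% | 0.04 | under 5% | yes |
| South | 3,504 | 7.6% | 0.08 | under 10% | yes |
| East, West | 3,066 | 8.1% | 0.08 | under 10% | yes |
| North | 2,190 | 9.6% | 0.10 | under 10% | yes |
| Kigali province | 1,644 | 11.1% | 0.11 | under 10% | **no** |
| District, standard | 438 | 21.5% | 0.22 | under 20% | **no** |
| District in Kigali | 548 | 19.2% | not shown | under 20% | yes |

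The printed CVs reproduce; the two bounds do not. North's 0.10 is a rounded 9.6% and is not a failure. The district table is captioned 440 women, but n = 440 gives 21.45%, which would round to 0.21. The printed 0.22 fits n = 438 (21.50%). The bound is missed with either figure.

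**Where the bounds start to hold.** Setting CV = r and solving for P gives P = 1 / (1 + n r² / 2.25).

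- Standard district, r = 0.20: 1 / (1 + 438 × 0.04 / 2.25) = 1 / 8.787 = 11.4%.
- Kigali district, r = 0.20: 1 / (1 + 548 × 0.04 / 2.25) = 9.3%.
- Kigali province, r = 0.10: 1 / (1 + 1,644 × 0.01 / 2.25) = 1 / 8.307 = 12.04%.

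**At the 15% level.** With n = 438, CV = 1.5 × √(0.85 / (438 × 0.15)) = 17.1% (printed 0.17). The 15% threshold used elsewhere is therefore consistent with the tables.

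**Sample needed to keep the text as it stands.** n = 2.25 × 9 / r². A standard district would need 506.25, so at least 507 women. Kigali province would need more than 2,025.

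**Could 1.5 be a variance inflation (Deff)?** The multiplier would then be √1.5 = 1.225. A standard district would have 17.6% and Kigali province 9.1%, both inside the bounds. But the formula multiplies the standard error by Deft, and the tables reproduce only with a multiplier of 1.5, so this reading does not rescue the text.

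**The case against.** The strongest reply is that little depends on the sentence. The correct CVs are printed directly below it. The threshold for women's district indicators is given elsewhere as 15%, and Appendix B applies that to most of them with a 20% relative standard error. At 15% a standard district has 17.1%, so a women's indicator at 10% or 11% is already below that floor. Sampling errors are also to be calculated for selected indicators in each province. One province of five misses, by 1.1 points. The standard districts miss by 1.5 points at exactly 10% and are inside the bound from 11.4%. All of this stands, and it limits the severity. It does not make the sentence true, and the protocol states no comparable floor for Kigali province.

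Two stronger readings are tempting, and the documents do not support them.

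- **That the national bound of 5% also fails, because men and biomarkers are measured in half the households.** The bounds are introduced as precision for the women's survey, where 3.9% meets the bound. Carrying Deft = 1.5 over to the half-sample would give 5.6% for 6,500 men and 5.5% for 6,735 women (half of 13,470), but that Deft is an assumption. The only half-sample precision table, for HIV testing, implies about 1.2. For Rwanda, 0.061 / √(0.97 / (12,207 × 0.03)) = 1.19; for East, 0.142 / √(0.975 / (2,779 × 0.025)) = 1.20. At Deft = 1.2 the figures are 4.5% and 4.4%. Failure needs a Deft above about 1.34 (men) or 1.37 (women). The HIV value need not carry over to other indicators, so the documents settle the matter neither way.
- **That the bounds determined the allocation, so the design itself is in doubt.** The protocol attributes the equal allocation to the request for district results within a tight total sample, and the larger Kigali districts to lower fertility. It cites no relative standard error as the source of 438 or 548.

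**Conclusion.** The contradiction is real, and the protocol alone establishes it. At P = 10% the province bound fails in Kigali (11.1% against under 10%), and the district bound fails in 27 of 30 districts (21.5% against under 20%). The other four provinces, the three Kigali districts and the national women's sample meet their bounds.

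The conclusion rests only on the protocol's formula, its Deft of 1.5 and its planned numbers of interviews. The error lies in the two prose bounds; the tables, the allocation and the 15% floor agree with one another. The 15% sentence is best read as a stricter adequacy threshold and not as a rival value for the same quantity, since it names no relative standard error itself. This is a minor to moderate correction of a stated precision figure.

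**What to change.** Restate the bounds in Expected survey precision so that they match the tables, along these lines:

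- **Scope.** All three bounds, including the national one, refer to the full women's sample.
- **National.** Under 5% at P of 10% or more (unchanged).
- **Province.** Under 10% at P of 10% or more, except Kigali, where it is about 11% at P = 10% and falls below 10% from just above P = 12%.
- **District.** About 22% at P = 10% in the districts with 438 women, and under 20% from about P = 12%. In the three Kigali districts it is about 19% at P = 10%. For most women's indicators the district floor is 15%, as in Structure of the sample and the sampling procedure and in Appendix B. Limit this remark to those indicators, because the Appendix B minima range from 5% to 50%.

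The district table caption could read 438 instead of 440, since 438 is the figure that gives the printed 0.22.

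The cost is wording only. Sample size, allocation, fieldwork and analysis stay as they are. Raising the sample to meet the present text is not a realistic alternative, because the protocol describes the current district size as the largest allowable.

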#### **Expected survey precision at national level according to indicator levels**

(With 13470 women interviews and assuming a design effect of Deft=1.5)

Indicator level	SE	CV	%95 Confidence limits	
			Lower	Upper
0.10	0.004	0.04	0.092	0.108
0.15	0.005	0.03	0.141	0.159
0.20	0.005	0.03	0.190	0.210
0.25	0.006	0.02	0.239	0.261
0.30	0.006	0.02	0.288	0.312

#### **Expected precision at province level for an indicator P=10%**

(Assuming a design effect of Deft=1.5)

Province	# of women interviews	SE	CV	%95 Confidence limits	
				Lower	Upper
East	3,066	0.008	0.08	0.084	0.116
Kigali	1,644	0.011	0.11	0.078	0.122
North	2190	0.010	0.10	0.081	0.119
South	3,504	0.008	0.08	0.085	0.115
West	3,066	0.008	0.08	0.084	0.116

### Expected precision at district for different indicator levels

(With an estimate of 440 women interviews and assuming a design effect of Deft=1.5)

Indicator level	SE	CV	%95 Confidence limits	
			Lower	Upper
0.10	0.022	0.22	0.057	0.143
0.15	0.026	0.17	0.099	0.201
0.20	0.029	0.14	0.143	0.257
0.25	0.031	0.12	0.188	0.312
0.30	0.033	0.11	0.234	0.366

As for the precision of HIV testing, since Rwanda is a low HIV prevalence country, HIV testing must be included in a high proportion of the households sampled for the survey. HIV testing will be conducted in the sub-sample households for men survey; consisting one of every two households selected for the household and women survey. The sample for the RDHS-V is designed to measure the prevalence of HIV within  $\pm 0.5$  percentage points at the national level and generally within  $\pm 1$  percentage point at the province level. The confidence interval for Kigali City is expected to be somewhat larger than that of the other provinces due to its higher prevalence estimate; however, the relative error for the Kigali City estimate is expected to be equal to or less than that of the other provinces. Compared to the last RDHS-IV (2010), the precision of HIV testing will be similar due to the same sample size.

### Expected precision for HIV testing at national level and province level for women and men together, based on the HIV testing results of RDHS-IV (2010)

Province	Expected # of HIV tests	Expected HIV prevalence	SE	CV	95% Confidence limits	
					Lower	Upper
East	2,779	0.025	0.004	0.142	0.018	0.032
Kigali City	1,488	0.067	0.008	0.116	0.051	0.083
North	1,985	0.020	0.004	0.189	0.012	0.028
South	3,176	0.027	0.003	0.128	0.020	0.034
West	2,779	0.032	0.004	0.125	0.024	0.040
Rwanda	12,207	0.030	0.002	0.061	0.026	0.034

### Selection probability and sampling weight

Due to the non-proportional allocation of the sample to the different provinces and to their districts and the possible differences in response rates, sampling weights will be required for any analysis using RDHS 2014-15 data to ensure the actual representative of the survey results at national level and as well as at domain level. Since the RDHS 2014-15 sample is a two-stage stratified cluster sample, sampling weights will be calculated based on sampling probabilities separately for each sampling stage and for each cluster. We use the following notations

$P_{1hi}$ : first-stage sampling probability of the  $i^{th}$  EA in stratum  $h$

$P_{2hi}$ : second -stage sampling probability within the  $i^{\text{th}}$  EA (household selection)

Let  $a_h$  be the number of EAs selected in stratum  $h$ ,  $M_{hi}$  the total population according to the sampling frame in the  $i^{\text{th}}$  village, and  $\sum M_{hi}$  the total population in the stratum  $h$ . The probability of selecting the  $i^{\text{th}}$  EA in the RDHS 2014-15 sample is calculated as follows:

$$\frac{a_h M_{hi}}{\sum M_{hi}}$$

Let  $b_{hi}$  be the proportion of households in the selected segment compared to the total number of households in the EA  $i$  in stratum  $h$  if the EA is segmented, otherwise  $b_{hi} = 1$ . Then the probability of selecting village  $i$  in the sample is:

$$P_{1hi} = \frac{a_h M_{hi}}{\sum M_{hi}} \times b_{hi}$$

A RDHS 2014-15 cluster is either an EA or a segment of a large EA. Let  $L_{hi}$  be the number of households listed in the household listing operation in the cluster  $i$  in stratum  $h$ , let  $g_{hi}$  be the number of households selected in the cluster. The second stage's selection probability for each household in the cluster is calculated as follows:

$$P_{2hi} = \frac{g_{hi}}{L_{hi}}$$

The overall selection probability of each household in cluster  $i$  of stratum  $h$  is therefore the production of the two stages selection probabilities:

$$P_{hi} = P_{1hi} \times P_{2hi}$$

The design weight for each household in cluster  $i$  of stratum  $h$  is the inverse of its overall selection probability:

$$W_{hi} = 1 / P_{hi}$$

A spreadsheet containing all sampling parameters and selection probabilities will be prepared to facilitate the calculation of the design weights. Design weights will be adjusted for household non-response and as well as for individual non-response to get the sampling weights, for women and men surveys respectively. The differences of the household sampling weights and the individual sampling weights are introduced by individual non-response. The final sampling weights will be normalized in order to give the total number of un-weighted cases equal to the total number of weighted cases at national level, for both household weights and individual weights, respectively. The normalized weights are relative weights which are valid for estimating means, proportions and ratios, but not valid for estimating population totals and for pooled data. The sampling weights for HIV testing are calculated in a similar way, but the normalization of the individual sampling weights is different compared to the individual survey weights. The HIV testing weights are normalized for males and females together at national level, in order that the HIV prevalence calculated for males and females together is valid.

Sampling errors will be calculated for selected indicators for the national sample, for the urban and rural areas separately, and for each of the five provinces.

All men aged 15-59 years and all women aged 15-49 years in 50% of households will also be

asked to consent to be measured for height and weight, and tested for HIV. Children under 5 years of age residing in the household sub-sample will be eligible to be measured and weighed in order to determine their nutritional status. Children under five years of age and women 15-49 will be eligible for the malaria and anemia tests. In addition, children 0-14 years in 25% of household will be tested for HIV.

Before the beginning of the survey, an updating of the EAs selected will be undertaken (mapping and enumeration) so that updated household lists will be made available for the selection of households for the sample. The updating will be undertaken by 17 teams, each composed of two enumerators, for a period of 3 months. Four staff members from NISR will be assigned to supervise the activities of the enumeration teams. NISR will organize a training session for field staff in the 7 days prior to the commencement of field work. The Enumeration Manual of the DHS program will be adapted and utilized during this training. Office and field supplies, office space, and vehicles for field activities will be made at the disposal of the enumeration staff. Twenty three (one per each team and one per each supervisor, and two for coordination) vehicles will be needed for the work of updating the mapping and carrying out the numbering.

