### Anticipated products or inventions resulting from the study and their use: (Disseminating results to public)

Three reports will be written based on results from the RDHS-V: a preliminary report on the main results of the survey, a final report, and a summary report.

The preliminary report will be published about one month after the end of fieldwork. It will be brief and will include about fifteen tables defined in the model preliminary report of the DHS program. The text that accompanies the report will be brief and will not exceed ten pages. This report will be in English, and will be written jointly by NISR and MOH in collaboration with personnel from ICF International. About 250 copies will be printed. NISR will be in charge of distribution at the national level and ICF International will ensure a limited dissemination at the international level.

The final report will be published in the 6 months following the end of fieldwork. This report will be in a single volume and will have about 540 pages. The tables presented will be drawn up from the tables of the Final Report of the DHS Project. The tables will be drawn up by NISR, MOH, and the NRL in collaboration with ICF International. The report will be in English and will be written jointly by personnel from NISR, other Rwandan institutions involved in the project including MOH, the RBC/NRL Division, NISR and ICF International personnel. In addition, three members from the technical staff of the RDHS-V will make a visit to the main office of ICF International in Rockville, Maryland, for a period not to exceed three weeks in order to finalize this report in consultation with ICF International personnel. ICF International will print 1000 copies of the final report. ICF International will keep around 200 copies of this report and will ensure dissemination at the international level. ICF International will send 800 copies to NISR who will be responsible for the

distribution of copies to institutions and organizations in Rwanda who are interested in the results.

Tables that summarize indicators at the district level will be provided in an appendix of the final report.

As soon as the final report and the summary report are ready, NISR will organize a national seminar to present the results. ICF International will lend its assistance to the preparation of the seminar and will actively participate in it.

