b. Recent sexual activity: men	(ever had sex/sex within last 4 weeks/never had sex)	≥30%	2010 RDHS
Maternal and child health			
a. Antenatal care:	(trained provider/non trained provider; no care)	≥30%	2010 RDHS
b. Component of antenatal care:	(some components with prevalent > 30%)	≥30%	2010 RDHS
c. Tetanus injection;	(none/one injection/2+ injection)	≥30%	2010 RDHS
d. Place of delivery;	(health facility/home)	≥20%	2010 RDHS
e. Assistant during delivery:	(trained personnel/untrained; relative; no one)	≥20%	2010 RDHS
f. Vaccination in children 12-23	(Fully immunized)	≥50%	2010 RDHS
g. Prevalence of childhood illnesses	(yes/no); fever (yes/no); and diarrhea (yes/no) in past 2	≥15%	2010 RDHS
Malaria			
a. Possession of mosquito net:	any net; ever-treated net; LLIN (at least one/2+)	≥15%	2010 RDHS
b. Use of mosquito net	by children 0-59 months	≥20%	2010 RDHS
c. Use of mosquito net	by women	≥15%	2010 RDHS
Breastfeeding and nutrition of mothers			
a. Initial breastfeeding	(ever breastfed; within 1st hour, within 1st day;	≥20%	2010 RDHS
b. Prevalence of ANY anemia in	(yes/no)	≥35%	2010 RDHS
c. Prevalence of ANY anemia in	(yes/no)	≥30%	2010 RDHS
HIV/AIDS related knowledge, attitudes, and behavior			
a. Knowledge of AIDS: women and	has heard of AIDS	≥30%	2010 RDHS
b. Knowledge HIV prevention:	using condom (1)	≥15%	2010 RDHS
	limiting sex to one uninfected partner (2)	≥15%	2010 RDHS
	both (1) and (2)	≥15%	2010 RDHS
	abstaining from sex (3)	≥15%	2010 RDHS

c. Knowledge HIV prevention: men	using condom (1)	>30%	2010 RDHS
	limiting sex to one uninfected partner (2)	>30%	2010 RDHS
	both (1) and (2)	>30%	2010 RDHS
	abstaining from sex (3)	>30%	2010 RDHS
d. Knowledge about AIDS: women	healthy looking person can have AIDS (1)	≥15%	2010 RDHS
	AIDS cannot be transmit through mosquito bites (2)	≥15%	2010 RDHS
	AIDS cannot be transmit through supernatural means	≥15%	2010 RDHS
	A person cannot become infected by sharing with food with a person who has AIDS (4)	≥15%	2010 RDHS
	All (1), (3), and (4)	≥15%	2010 RDHS
e. Knowledge about AIDS: men	healthy looking person can have AIDS (1)	≥30%	2010 RDHS
	AIDS cannot be transmit through mosquito bites (2)	≥30%	2010 RDHS
	AIDS cannot be transmit through supernatural means	≥30%	2010 RDHS
	A person cannot become infected by sharing with food (1), (3), and (4)	≥30%	2010 RDHS
		≥30%	2010 RDHS
f. Knowledge of PMTCT: women	HIV can be transmitted by breastfeeding (1)	≥15%	2010 RDHS

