	Risk of MTCT can be reduce by taking ARVs (2)	≥15%	2010 RDHS
	Both (1) and (2)	≥15%	2010 RDHS
g. Knowledge of PMTCT: women	HIV can be transmitted by breastfeeding (1)	>30%	2010 RDHS
	Risk of MTCT can be reduce by taking ARVs (2)	>30%	2010 RDHS
	Both (1) and (2)	>30%	2010 RDHS
h. Accepting attitude: women	Willing to care for family member with AIDS	≥15%	2010 RDHS
	Buying fresh vegetable from vendor with AIDS	≥15%	2010 RDHS
	Agreeing that female teacher with AIDS and not sick	≥15%	2010 RDHS
	Would not keep a secret of family member with AIDS	≥15%	2010 RDHS
i. Accepting attitude: men	Willing to care for family member with AIDS	>30%	2010 RDHS
	Buying fresh vegetable from vendor with AIDS	≥30%	2010 RDHS
	Agreeing that female teacher with AIDS and not sick	≥30%	2010 RDHS
	Would not keep a secret of family member with AIDS	>30%	2010 RDHS
j. Negotiating safer sex with a husband if he has STD: women	Refusing sex (1)	≥15%	2010 RDHS
	Asking to use condom (2)	≥15%	2010 RDHS
	Both (1) and (2)	≥15%	2010 RDHS
k. Support of education about condom use in children: women	(Yes/no)	≥15%	2010 RDHS

l. Support of education about condom use in children: men 18-		≥30%	2010 RDHS
m. Ever tested for HIV: women	(yes/no)	>15%	2010 RDHS
n. Ever tested for HIV: men	(yes/no)	≥30%	2010 RDHS
o. Received counseling during	(yes/no)	≥35%	2010 RDHS
p. Knowledge about AIDS in youth	Knowledge of AIDS and a source of condom	≥25%	2010 RDHS
q. Never had sex among youth (15-	Knowledge of AIDS and a source of condom	≥45%	2010 RDHS
*Each category of indicators must be at least at this level or higher allowing for the computation at the district-level with relative standard error of 20%. These indicators were selected based on the 2010 RDHS. If the levels of indicators drop lower than the			

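### District estimates are to be published against a 20% relative standard error, but districts are not among the domains for which sampling errors will be calculated, and one Appendix B floor contradicts the sampling section

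*Protocol*

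**What the plan says.** Three parts of the protocol bear on district precision.

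- **Where errors are calculated.** *Selection probability and sampling weight* states: "Sampling errors will be calculated for selected indicators for the national sample, for the urban and rural areas separately", and the sentence ends with the five provinces. Districts are not in that list, and no other section provides for them.
- **What is published.** The dissemination section (E) promises: "Tables that summarize indicators at the district level will be provided in an appendix of the final report".
- **The criterion for publishing.** The footnote to Appendix B says each indicator category "must be at least at this level or higher allowing for the computation at the district-level with relative standard error of 20" per cent. The floors are attributed to the 2010 survey and range from 5% to 50%.

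Two floors matter here. The item "g. Prevalence of childhood illnesses" is listed at 15% or more. Educational attainment of the female and male household populations is listed at 5% or more. *Structure of the sample and the sampling procedure*, however, describes district precision as adequate for women's indicators above 15% "and for children (under five) indicators above 20" per cent.

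**The concern.** A minimum prevalence stands in for precision only if the sample size and the design effect turn out as planned. Both vary by district and by indicator, and Deft for a household-clustered item can differ a good deal from a single planning value. If no standard error is computed for a district, the sponsor cannot tell whether a published figure meets the sponsor's own criterion, and a reader cannot judge whether two districts differ.

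The stakes are highest at this level because precision is weakest there. By the protocol's own district table, an indicator at 15% carries limits of 9.9% to 20.1%. District figures printed without errors invite ranking on differences that sampling noise could produce.

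The childhood-illness floor is a separate matter: two sections give different thresholds for the same population and the same reporting level.

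**Working it through.** **Inputs.** *Expected survey precision* gives the method: "The relative standard error (CV) for a proportion P is calculated by the following formula", that is, CV = Deft × √(P(1−P)/n) / P, or equivalently Deft × √((1−P)/(P·n)). Deft is 1.5. Expected women's interviews per district are 438 outside Kigali and 548 in Kigali (27 × 438 + 3 × 548 = 13,470, as stated). Households number about 12,800, or 12,800/30 ≈ 427 per district on average. Men's interviews number about 6,500, or about 217 per district on average.

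**Reproducing the plan's district table** (n = 440, Deft 1.5):

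| P | RSE computed | CV stated |
|---|---|---|
| 0.10 | 0.2145 | 0.22 |
| 0.15 | 0.170 | 0.17 |
| 0.20 | 0.143 | 0.14 |
| 0.25 | 0.124 | 0.12 |
| 0.30 | 0.109 | 0.11 |

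The first row reads 0.215, hence 0.22, with n = 438. The formula and inputs are therefore the ones the protocol used.

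**Main floors at Deft 1.5:**

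- Women, P = 15%, n = 438: 1.5 × √(0.85/(0.15 × 438)) = 17.1%.
- Men, P = 30%, n = 217: 15.6%.
- Household characteristics, P = 20%, n = 427: 14.5%.

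All three meet 20%.

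**Margin on Deft.** For women at 15% with n = 438, the RSE reaches 20% when Deft = 0.20 / √(0.85/(0.15 × 438)) = 0.20/0.1137 = 1.76. At Deft 1.8 it is 20.5%.

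**Sample needed for an RSE of 20%.** n = Deft² × (1−P)/(P × 0.20²) = 2.25 × ((1−P)/P)/0.04:

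- P = 5%: 1,069
- P = 15%: 319
- P = 20%: 225

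**Childhood illness at 15%.** The expected number of under-fives per district is not stated, so a range is needed:

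| Children per district (assumed) | RSE at P = 15% |
|---|---|
| 225 | 23.8% |
| 309 | 20.3% |
| 319 | 20.0% |
| 400 | 17.9% |

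The 225 row assumes that the 20% threshold in the sampling section is the exact point where the RSE reaches 20%. The 309 row assumes that adequate means the same RSE for children at 20% as for women at 15%: 2.25 × (0.80/0.20)/0.1706² = 309.

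**Household education at 5%.** The base is the household population of one sex, not the interviewed women. The 1,069 persons needed are 1,069/427 ≈ 2.5 per household. Household size is not stated, so again a range:

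| Persons of one sex per household (assumed) | n per district | RSE at P = 5% |
|---|---|---|
| 1.5 | 640 | 25.9% |
| 2.0 | 853 | 22.4% |
| 2.25 | 960 | 21.1% |
| 2.5 | 1,067 | 20.0% |

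**The case against.** The strongest reply is that the list of domains is positive and excludes nothing in words. A footnote defers the detailed sampling design to a later visit, tabulation follows the standard DHS plan, and further domains for variance estimation could be set in an analysis plan. That limits how much can be read into the omission. It does not remove the point: the protocol itself fixes the list and the district criterion, and the first does not serve the second.

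Some stronger readings are tempting but not supported:

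- *Districts are the only figures published without error measures.* They are not. Sampling errors cover selected indicators only, and the HIV table shells in Appendix A show percentages and numbers with no error column.
- *The criterion is never checked on the data.* The Appendix B footnote is cut off in the available text just where it turns to indicator levels falling. It may contain a rule applied to observed prevalence. What can be said is that realised district error is not calculated under the stated list.
- *The 20% threshold for children implies about 225 children, so the 15% floor fails.* The protocol calls precision adequate above that level and does not equate it with an RSE of exactly 20%. The same reasoning applied to women's 15% would imply 319 interviews, whereas 438 are planned.
- *The 5% education floor fails.* That depends on a household size the protocol does not give, and on Deft. With 900 persons and Deft 1.2 the RSE would be 17.4%.

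It is also fair to say that nothing in the protocol indicates a Deft above 1.76. That figure shows the margin and does not predict a breach.

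**Conclusion.** The point holds in two parts. First, the protocol publishes district estimates under a 20% RSE criterion but leaves districts out of its stated sampling-error calculation. Compliance therefore rests on prevalence floors and an assumed Deft of 1.5. At that Deft the main floors comply (17.1% for women, 15.6% for men, 14.5% for households), so the gap is one of verification and not a general failure of the floors. For women at 15% in a 438-interview district, the margin is used up at Deft 1.76.

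Second, the 15% floor for childhood illness contradicts the 20% threshold in the sampling section. That contradiction needs no outside figure. Whether the 15% floor misses an RSE of 20% is not established: it does with fewer than 319 children per district and does not with more, at Deft 1.5.

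The 5% education floor is marginal. It meets 20% only at about 2.5 or more persons of one sex per household at Deft 1.5, and should be rechecked rather than declared wrong.

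**What to change.** - In *Selection probability and sampling weight*, extend the sampling-error sentence to cover all thirty districts for the Appendix B indicators.
- In the district appendix of the final report, show the achieved RSE or 95% confidence interval beside each estimate, and flag or suppress those above the stated 20%.
- Reconcile the childhood-illness floor with the sampling section: either raise it to 20%, or state the expected number of under-fives per district that supports 15% (at least 319 at Deft 1.5).
- Recheck the 5% education floor against the expected household population of each sex per district, stating the household size used.

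The cost is small. Districts are already the sampling strata with independent selection, and sampling errors are already planned for other domains, so this means extra runs of the same program. A few district cells may be flagged or suppressed. Neither the sample nor the fieldwork changes.
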